5.6 Publishing the Study Data

Upon completion of the clinical study, it is the intention of the Investigators and Study Sponsor to report the performance characteristics (sensitivity, specificity, positive predictive value, negative predictive value) of ^{11}C -choline PET/CT and PET/MRI in the detection of metastatic prostate cancer in patients with biochemical relapse of prostate cancer after primary treatment in a prospective manner and compare to the performance characteristics with those of conventional imaging. We will also report the performance characteristics of ^{11}C -choline PET/CT compared to ^{11}C -choline PET/MRI and the combination of ^{11}C -choline PET/CT and PET/MRI. Finally, we will report the demographic, clinical, and pathologic factors that predict a positive ^{11}C -choline PET/CT or PET/MRI in the two study groups.

6.0 CONTRAINDICATIONS, WARNINGS AND PRECAUTIONS

6.1 Contraindications

None

6.2 Warnings and Precautions

- Imaging errors have been reported during previous clinical studies with ^{11}C -choline PET and PET/CT imaging. A negative image does not rule out the presence of recurrent prostate cancer and a positive image does not confirm the presence of recurrent cancer. ^{11}C -choline uptake is not specific

Investigatory New Drug
**Clinical Trial Protocol:
Choline C11 Injection**

Revision Date: _01/30/2015

Page 20 of 59

for prostate cancer and may occur with other types of cancer, such as lung carcinoma and brain tumors.

- Blood PSA levels < 2 ng/mL have been associated with poor performance ^{11}C -choline PET imaging, with indications of higher numbers of false positive and false negative results.
- Tissue inflammation as well as prostatic hyperplasia have been associated with false positive ^{11}C -choline PET images.
- Concomitant colchicine or androgen-deprivation therapeutic drugs, such as luteinizing hormone-releasing analogs and anti-androgen drugs, may interfere with ^{11}C -choline PET imaging. One published report of ^{18}F methylcholine PET imaging indicated that discontinuation of colchicine for two weeks resolved the colchicine effect. The impact of discontinuation of androgen-deprivations therapy upon ^{11}C -choline PET imaging has not been established.

6.3 Limitation of Use

^{11}C -choline PET imaging is NOT a replacement for histologic verification of relapsed prostate cancer.

7. ASSESSMENT OF SAFETY

7.1 Radiation Safety – Drug Handling

^{11}C -choline is a radioactive drug and will be handled with appropriate safety measures to minimize radiation exposure during administration. The use of waterproof gloves and effective shielding when handling ^{11}C -choline will be required. Radiopharmaceuticals, such as ^{11}C -choline will only be used by or under the control of physicians who are qualified by specific training and experience in the safe use and handling of radioactive materials, and whose experience and training have been approved by the appropriate governmental agency authorized to license the use of radionuclides.

^{11}C -choline will be delivered to a Certified Nuclear Medicine Technician (CNMT) or equivalently qualified personnel in individual, single dose syringes contained within a NRC/DOT approved syringe shield specifically designed for minimizing radiation exposure during handling. The safe handling of Radioactive Material will be as defined within the Sponsors' radioactive material license issued by the Illinois Energy Management Agency (IEMA), the state nuclear regulatory agency responsible for radioactive material within the State of Illinois.

7.2 Radiation Risks – Patients

¹¹C-choline contributes to a patient's overall long-term cumulative radiation exposure. Long-term cumulative radiation exposure is associated with an increased risk for cancer. Safe handling should be ensured to minimize radiation exposure to the patient.

7.3 Indications and Usage

¹¹C-choline is a radioactive diagnostic agent initially approved for use by the U.S. Food & Drug Administration in 2012 for positron emission tomography (PET) imaging of patients with suspected prostate cancer relapse and non-informative bone scintigraphy computed tomography. It is dispensed and administered under the reference listed drug (RLD) label: 233155. For the purposes of this study, ¹¹C-choline will be produced, dispensed and administered according to the prescribing information as detailed in the approved drug labeling.

7.4 Patient Safety Evaluations

Patient safety will be evaluated prior to participation in the study and before execution of each of the imaging protocols by screening process.

7.5 Safety Review

An Institutional Review Board (IRB) will review the protocol of this study for safety and effectiveness prior to its implementation. The IRB will convene to approve the Clinical Protocol as defined in this document as well as the Informed Consent, as defined in the U.S. Code of Federal Regulations, 21 CFR 50 and 56. The IRB will also meet on an as needed basis to examine any potential safety issues and the overall conduct of the trial.

8.0 ADVERSE REACTIONS

8.1 Adverse Reactions, General

Exclusive of an uncommon, mild injection site reaction, no adverse reactions to ¹¹C-choline have been reported.

8.2 Allergic Reactions

As with any injectable drug product, allergic reactions and anaphylaxis may occur. Emergency

Investigatory New Drug
**Clinical Trial Protocol:
Choline C11 Injection**

Revision Date: _01/30/2015

Page 22 of 59

resuscitation equipment and personnel will be immediately available during and within a reasonable time soon after the imaging procedures defined in the clinical protocol.

8.3 IND Safety Reporting Requirements

8.3.1 21 CFR 312

The U.S. Code of Federal Regulations, section 21 CFR 312, defines the conditions within which Adverse Events (AE) and Severe Adverse Events (SAE) are reported to the FDA. For the purposes of this study, the sponsor will be responsible for reporting AEs and SAEs to the FDA as defined by these regulations.

8.3.2 Adverse Events

Adverse Event means any untoward medical occurrence associated with the use of a drug in humans, whether or not considered drug related.

An adverse event, also referred to as an adverse experience, can be any unfavorable and unintended sign (e.g., an abnormal laboratory finding), symptom, or disease temporally associated with the use of a drug, and does not imply any judgment about causality.

An adverse event may be any of the following:

1. A new illness
2. An exacerbation or a sign or symptom of the underlying condition under treatment or of a concomitant illness
3. Unrelated to participation in the clinical study or an effect of the study radiopharmaceutical or comparator drug
4. A combination of 1 or more of the above factors

An exacerbation of a pre-existing condition/illness is defined as a more frequent occurrence or as an increase in the severity of the pre-existing condition/illness during the study. Planned or elective surgical procedures for pre-existing conditions that have not worsened are not AEs. However, any complication that occurs during planned or elective surgery is an AE. Conditions leading to unplanned surgical procedures may be AEs.

Investigatory New Drug
**Clinical Trial Protocol:
Choline C11 Injection**

Revision Date: _01/30/2015

Page 23 of 59

The period of observation for collection of (treatment-emergent) AEs extends from the time the subject takes the first dose of study radiopharmaceutical until their exit from the study. The patient will be called within 24 hours after the protocol scan to assess any AEs and SAEs.

In the event of an adverse event, the Investigator is required to file an Adverse Event Report using the AE Report Form to the sponsor within a reasonable period of time, but no later than 3 days after the event has been recognized by the Investigator. The Sponsor contact information for reporting AEs is listed in section 8.3.7 below.

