5. Patients entered into the study will undergo a ^{11}C -choline PET CT scan and MRI scan. The CT scan will be performed with intravenous contrast unless deemed unsafe by lab values. The CT and MRI images will be evaluated for evidence of metastatic prostate cancer. The ^{11}C -choline PET CT and MRI images will be evaluated for evidence of metastatic prostate cancer. Unequivocal evidence of metastasis on both conventional imaging and ^{11}C -choline PET will be considered a true positive. Evidence of metastasis on conventional imaging or ^{11}C -choline PET will be confirmed with biopsy or surgical pathology when possible, or by response to treatment on subsequent imaging. If confirmation of metastasis is not achievable by biopsy or surgical pathology, then confirmation will be achieved with ^{11}C -choline PET CT and MRI images obtained 3 months after treatment conclusion. Rates of confirmed metastasis between conventional CT and MRI images will be compared with the ^{11}C -choline PET CT and MRI images.
6. Upon conclusion of each imaging protocol, the referring physician will receive written documentation of the results. At this time, the patient will be considered off study and no further follow up is required.

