8.4 Patient Monitoring

Patient subjects will be monitored throughout the imaging process during the administration of the imaging agents and immediately thereafter. Patient subjects will be instructed to inform the study physician and/or study coordinator of any AEs that may occur at any time during the study after the injection of the imaging agents. Patients will be contacted within 24 hours after the investigational scan to assess any AEs/SAEs. They will also be contacted again when imaging report is finalized and sent to their treating physician.

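### In the comparison protocol, the exit rule closes adverse-event collection before the repeat 11C-choline injection that Section 5.1 itself calls for

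*Combined protocol and SAP*

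**What the plan says.** All references are to the comparison protocol in the combined document, unless stated otherwise.

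- **AE window.** Section 8.3.2 says that the collection period "extends from the time the subject takes the first dose of study radiopharmaceutical until their exit from the study".
- **Exit.** Section 5.1 item 6 reads "Upon conclusion of each imaging protocol, the referring physician will receive written documentation of the results", and continues: "At this time, the patient will be considered off study and no further follow up is required".
- **Confirmation.** Section 5.1 item 5, directly before the exit rule, says that evidence of metastasis "will be confirmed with biopsy or surgical pathology when possible, or by response to treatment on subsequent imaging". If tissue cannot be obtained, confirmation is to come from 11C-choline "PET CT and MRI images obtained 3 months after treatment conclusion".
- **Planned contact.** Section 8.3.2 states "The patient will be called within 24 hours after the protocol scan to assess any AEs and SAEs", and Section 8.4 states "Patients will be contacted within 24 hours after the investigational scan to assess any AEs/SAEs". Section 8.4 adds a second contact when the report is finalized and sent, without giving its purpose.

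**The concern.** Items 5 and 6 of Section 5.1 do not fit together. Item 5 asks for a scan that can take place only after the first report, after treatment, and after a further three months. Item 6 ends participation and follow-up at the first report. Because Section 8.3.2 ties AE collection to exit, the window closes before a second dose of the investigational drug that the protocol itself directs.

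The protocol thought a call within 24 hours worth making after the first injection, and it gives no reason to leave it out after a second. Section 8.2 notes that allergic reactions can follow any injectable product. As the text stands, whether a repeat injection is followed by AE collection and a call depends on how staff read two phrases, so men could be handled differently. At stake is completeness of safety capture for a repeat dose, not any accuracy result.

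**Working it through.** No figure in the plan bears on this point and no arithmetic is needed. The check is to put the events in order and then look for a clause that covers the repeat injection.

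**Order of events for a man whose finding cannot be confirmed from tissue**

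1. First 11C-choline injection and scan (5.1 item 5, 5.2). The AE window opens (8.3.2).
2. AE call within 24 hours (8.3.2, 8.4).
3. Report sent, with the second contact (8.4). The man is off study (5.1 item 6) and the AE window closes (8.3.2).
4. Treatment, given by his own physicians.
5. Three months after treatment ends: repeat 11C-choline injection and scan (5.1 item 5).

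Step 5 falls after step 3. Nothing in the protocol reopens the window or returns the man to the study.

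**Clauses that might cover step 5**

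- *The 24-hour call (8.3.2, 8.4).* Both sentences refer to a single scan. They could be taken to mean any scan under the protocol, but they do not say so.
- *The word each in 5.1 item 6.* It could mean the first scan and any repeat. However, Section 5.2, which is headed Imaging Protocols, lists two: PET/CT and whole-body MRI. Those are the natural referents. Even on the wider reading, the man has already been declared off study at the first report.
- *Patient self-report (8.4).* The instruction applies while the man is in the study.
- *Follow-up of AEs (4.2.2, 8.6).* Both concern events that are already open. Neither seeks new ones.
- *Reporting duties (8.3.4, 8.3.6, 8.5).* None is limited by exit, so an event that comes to the investigator's notice still has to be recorded and reported. None schedules a contact to find events.

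**Planned contacts after a repeat injection**

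- Literal reading: 0.
- Generous reading: 1 AE call within 24 hours, plus the contact at the report, whose purpose is not stated.

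**How many men.** The documents do not give the number and it cannot be derived from them. Several features could make it small. Item 5 accepts unequivocal findings on both conventional imaging and choline PET as true positives without further confirmation. It uses tissue where possible. Section 5.5 accepts response to treatment without requiring choline imaging. Section 1.3 lists observation as one management option, and an observed man has no end of treatment from which to count three months.

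**The case against.** The best case on the other side is that this is a wording matter with the real risks already handled. Much of that stands.

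- Section 8.2 requires resuscitation equipment and staff on hand during and soon after the imaging procedures, and Section 8.4 requires monitoring during administration and directly afterwards. Section 7.4 adds a safety check before each imaging protocol. A severe allergic reaction at a repeat scan would be met by these measures, not by a call the next day.
- Section 8.1 reports nothing beyond uncommon, mild injection-site reactions.
- Section 4.1 designates one hospital for imaging, so the documents give no basis for expecting different practice between sites. The ambiguity matters only for consistency from man to man.

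What these points do not remove is the conflict between items 5 and 6. The exit rule, applied as written, leaves the second dose outside planned AE collection.

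A reader might infer a wider gap, because Section 8.3.2 says that "any complication that occurs during planned or elective surgery is an AE" and no contact is planned after a confirmatory biopsy or operation. The documents do not support treating that as a defect. The same section defines an AE as an occurrence associated with use of a drug. Tissue sampling is done when possible, and under Section 5.4.1 the treating physician uses the scan to direct care. A complication of such a procedure is largely a matter of clinical care.

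**Conclusion.** The point holds and is minor. In the comparison protocol, AE collection and the 24-hour call do not expressly cover the repeat 11C-choline injection, because exit is set at the first report. The size is one missing planned AE call per repeat injection on the literal reading and none on the generous one, with an unknown and possibly small number of men affected.

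This rests on two assumptions: that a repeat scan done to satisfy item 5 is given under this protocol, and that exit in Section 8.3.2 means the off-study point in Section 5.1 item 6.

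Three further inferences should be resisted. Reactions to a repeat dose would not go unreported as a rule, since the reporting duties continue after exit; only solicited contact is missing. No planned accuracy estimate is biased by this, and no safety analysis is planned that it would distort. The expanded-access protocol is not affected, because its study procedures contain no confirmation step.

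**What to change.** 1. **Section 5.1 item 6.** State that a man for whom item 5 calls for a repeat 11C-choline scan exits when that scan has been reported and its 24-hour call made. All others exit at the first report, as now. It would help to add that, if the repeat scan is not done, he exits when that is recorded, so that no exit is left open.
2. **Sections 8.3.2 and 8.4.** State that the 24-hour AE call follows every 11C-choline injection given under this protocol, first or repeat. State also that no new AE collection is required between the first report and the repeat injection. This keeps events from intervening treatment out of the data, and it does no harm if the need for a repeat scan becomes clear only after the first report.

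The cost is a few sentences and one extra call per repeat injection, recorded on the existing AE form. No scans or patients are added. Section 4.1 draws men from a radius of about 300 miles, and some calls may not reach the patient; those should be recorded as not reached.

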8.3.3 Suspected Adverse Reactions

Suspected Adverse Reaction means any adverse event for which there is a reasonable possibility that the drug caused the adverse event. For the purposes of IND safety reporting, 'reasonable possibility' means there is evidence to suggest a causal relationship between the drug and the adverse event. A suspected adverse reaction implies a lesser degree of certainty about causality than adverse reaction, which means any adverse event caused by a drug.

It is the responsibility of the Sponsor to determine whether the Adverse Event should be classified as a Suspected Adverse Reaction.

8.3.4 Serious Adverse Events (SAEs)

An adverse event or suspected adverse reaction is considered "serious" if, in the view of either the investigator or sponsor, it results in any of the following outcomes:

- Death
- a life-threatening adverse event
- inpatient hospitalization or prolongation of existing hospitalization
- a persistent or significant incapacity or substantial disruption of the ability to conduct normal life functions
- a congenital anomaly/birth defect

Important medical events that may not result in death, be life-threatening, or require hospitalization may be considered serious when, based upon appropriate medical judgment, they may jeopardize the patient or subject and may require medical or surgical intervention to prevent one of the outcomes listed in this definition. Examples of such medical events include allergic bronchospasm requiring intensive treatment in an emergency room or at home, blood dyscrasias or convulsions that do not result in inpatient hospitalization, or the development of drug dependency or drug abuse.

Investigatory New Drug
**Clinical Trial Protocol:
Choline C11 Injection**

Revision Date: _01/30/2015

Page 24 of 59

In the event of an SAE, the Investigator is required to file an Adverse Event Report using the AE Report Form to the sponsor within 24 hours of the Investigator's recognition of the SAE. The Sponsor contact information for reporting AEs is listed in section 8.3.7 below.

8.3.5 Unexpected Adverse Events

An adverse event or suspected adverse reaction is considered "unexpected" if it is not listed in the investigator brochure or is not listed at the specificity or severity that has been observed. For example, under this definition, hepatic necrosis would be unexpected (by virtue of greater severity) if the investigator brochure referred only to elevated hepatic enzymes or hepatitis. Similarly, cerebral thromboembolism and cerebral vasculitis would be unexpected (by virtue of greater specificity) if the investigator brochure listed only cerebral vascular accidents. "Unexpected," as used in this definition, also refers to adverse events or suspected adverse reactions that are mentioned in the investigator brochure as occurring with a class of drugs or as anticipated from the pharmacological properties of the drug, but are not specifically mentioned as occurring with the particular drug under investigation.

8.3.6 Submission of IND Safety Reports

The sponsor must report in an IND safety report any suspected adverse reaction to study treatment (i.e., including active comparators) that is both serious and unexpected (21 CFR 312.32(c)(1)(i)). Before submitting an IND safety report, the sponsor needs to ensure that the event meets all three of the definitions:

- Suspected adverse reaction
- Serious
- Unexpected

If the Sponsor concludes that there is a significant likelihood that the imaging drug caused the adverse event, an IND Safety Report will be submitted to the FDA. In the event that the AE is found to be unexpected, fatal, or life-threatening, the sponsor is required to notify FDA and all participating investigators by fax or phone within 7 calendar days of the initial receipt of information. A written IND safety report must follow within 15 calendar days. All other AEs that are found to be causal to the imaging agent and are unexpected must be submitted in writing within 15 calendar days.

Each participating Investigator is responsible for submitting the IND Safety Report to the Investigator's Institutional Review Board (IRB) as per FDA regulations.

Investigatory New Drug
**Clinical Trial Protocol:
Choline C11 Injection**

Revision Date: _01/30/2015

Page 25 of 59

8.4 Patient Monitoring

Patient subjects will be monitored throughout the imaging process during the administration of the imaging agents and immediately thereafter. Patient subjects will be instructed to inform the study physician and/or study coordinator of any AEs that may occur at any time during the study after the injection of the imaging agents. Patients will be contacted within 24 hours after the investigational scan to assess any AEs/SAEs. They will also be contacted again when imaging report is finalized and sent to their treating physician.

8.5 Investigator Responsibility

The Investigator at the clinical center will completely and promptly record each adverse reaction. The Investigator should attempt, if possible, to establish a diagnosis based on the presenting signs and symptoms.

Unless directed otherwise per responsibilities outlined elsewhere in this document, the Investigator is required to report all adverse events to the Sponsor within 30 days of determination of the AE.

8.6 Follow Up

All unresolved AEs, Suspected Adverse Reactions and/or Severe AEs, will be followed by the responsible Investigator until resolved, the patient is stabilized, or the patient is lost to follow-up.

Investigatory New Drug
**Clinical Trial Protocol:
Choline C11 Injection**

Revision Date: _01/30/2015

Page 26 of 59

9.0 STUDY PATIENTS

9.1 Use in Specific Populations, General

This Phase III clinical study will include only men who have a confirmed diagnosis of prostate cancer.

9.1 Women

Choline C11 Injection is not indicated for use in women. Furthermore, there are no adequate and well controlled studies with Choline C11 Injection in pregnant women and the fetal radiation dose from a ¹¹C-choline PET imaging study is unknown. All radiopharmaceuticals, including Choline C11 Injection, have the potential to cause fetal harm. For the purposes of this clinical study allowing for expanded access to this diagnostic agent, female patients and/or pregnant women will not be allowed to participate.

